5.1 INCLUSION CRITERIA

In order to be eligible to participate in this study, an individual must meet the following criteria:

1. Parent or guardian willing to give informed consent, and children willing to give informed assent to participate in the study.
2. Must be actively enrolled and maintain eligibility in HUM00118950 to participate in the study.

5.2 EXCLUSION CRITERIA

An individual who meets the following criteria will be excluded from participation in this study:

1. Color blindness

5.3 LIFESTYLE CONSIDERATIONS

Patients will not be taking any psychotropic medications for 4 weeks prior to beginning the study with the exception of stimulants for ADHD. In such cases, patients will be required to maintain a stable dose of stimulant medication for 2 weeks prior to fMRI #1.

During the study, we will permit medication for 1) insomnia, e.g. trazodone, temazepam, melatonin, or non-benzodiazepine GABA-selective agents (at standard dosages) for as long as needed, and 2) agitation, e. g. lorazepam, clonazepam for up to 14 days. Initiation of allowable “rescue” medications will be considered AEs and data will be collected on them during the scheduled assessments and recorded in the Case Report Forms. NOTE: Initiation of other medications, prior to the end of the study, may be recommended by the study psychiatrist or requested by the patient. In this event, the patient will be withdrawn from the study and referred to clinical care.

5.4 SCREEN FAILURES

Screen failures are defined as participants who consent to participate in this study but are not subsequently assigned to the study intervention or entered in the study. Individuals who do not meet the criteria for participation in this trial (screen failure) because of meeting one or more exclusion criteria that are likely to change over time may be rescreened. Examples include the successful treatment of a previous affective disorder, and the lifting of physical activity restrictions previously in place. Rescreened participants will be assigned the same participant number as for the initial screening.

5.5 STRATEGIES FOR RECRUITMENT AND RETENTION

Subjects will be recruited from anxious youth in parent study. All participants will be approached to consent to the current protocol after they consent to the parent study. Age and gender match will be attempted. The following **recruitment and retention strategy** is specified in the parent study:

Recruitment will be from the outpatient psychiatry programs at the University of Michigan Health System, from multi-media advertisements (UMClinicalStudies.org, passive advertisements on social media sites and Craigslist Ann Arbor, Google Adword campaigns, print and electronic media, radio ads and flyers) and by referral from community clinicians. The recruitment process is designed to limit interference with clinical care and assure the informed participation of patient subjects. By obtaining a waiver of consent for screening purposes, recruitment is facilitated by pre-review of computer-based medical records to identify potential research participants who have contacted the Department of Psychiatry. In addition, we will scan UMClinicalStudies.org, the UM registry of individuals who are interested in participating in clinical research. Some of this screening will occur through the structured recruitment activities of University of Michigan's psychiatric department—for example, best practices alert. Paid advertising (e.g., radio, newspaper ads, utilizing Survey Research Organization (SRO)) may also be employed, if needed to reach recruitment goals.

The study sample will represent the normal to abnormal range of anxiety severity when considered across AY and LAY subjects. Thus, we will use a stratified recruitment strategy in which phone screens include administration of the DSM-Oriented Scale for Anxiety from the Child Behavior Checklist (CBCL) to enhance sampling across this range. Using this data, the study coordinator will track recruitment and enrollment of subjects with “high” (i.e., clinically significant anxiety, t-score >60), mid- (t-score 50-60) and low- (t-score <50) levels of symptom severity. Note that stratification of high, middle and low anxiety severity is intended only to facilitate recruitment across the full range of symptom severity. By contrast, all analyses will use linear regression, considering anxiety scores as continuous measures.

Clinic recruitment of pediatric subjects with Anxiety: We may recruit from three sources: 1) patients seeking treatment at the UM’s Child and Adolescent Anxiety Program (CAAP, directed by PI [name]); 2) primary pediatric UM outpatient clinics and community clinics; and 3) the community. Recruitment from this wide demographic will enable targeted enrollment of 210 CBT-eligible AY as well as 70 LAY with minimal to no anxiety. On average per year, we will enroll 47 subjects with high- to mid-range anxiety (i.e., CBT-eligible AY) and 16 with low-range anxiety. To achieve this goal, we will capitalize on high pediatric anxiety patient flow through CAAP (300/year) and an advertising campaign (Facebook, Twitter, Google AdWords, targeted flyering) modeled after [name] ongoing recruitment efforts for her R01 study of CBT for OCD (successfully enrolling 4 patients per month).

[name] is a member of the UM Psychiatry clinical staff and co-directs the Child Anxiety Clinic. Her role in the clinic primarily involves supervision of trainees who deliver direct clinical care to child anxiety patients, although [name] does see a small number of anxiety patients herself. If a dual role exists in which she is the treating clinician-principal investigator of a patient-potential subject, she will disclose this dual role and possible conflict of interest to them. Moreover, she will emphasize that participation is voluntary, that they do not have to participate, and the decision not to participate will not affect their care, now or in the future. A study coordinator (not [name]) will reiterate these points as part of the formal consent process. Clinicians outside of the study team may be asked to inquire if patients are interested in research participation, and if so, for permission for study team members to contact them. In addition, should a physician discuss with the study team a patient they feel likely eligible for the study, a study team member will outreach to the patient to offer information on the study with the clinician’s permission to do so.

Recruitment of clinic scheduled or wait-listed pediatric subjects with Anxiety: We will contact scheduled or wait-listed patients who look like they might have anxiety based on information from their electronic medical record. Then we will contact them by phone, [SECURE] email or MiChart patient portal, announcing our affiliation with the U-M Psychiatry Anxiety Disorders clinic, and ask them if they would be interested in hearing about a research study involving treatment. If they are, we will conduct our phone screen.

Recruitment of participants not being seen in the Department of Psychiatry: Through community advertisements, we will also screen, assess and enroll participants who are not followed in the Department of Psychiatry. Initial screening will occur in a telephone interview. In many cases, we will request records from outside providers to assess eligibility, using standard release of information forms. For potential participants who appear eligible, a face-to-face initial assessment will be scheduled. A similar process will occur with control subjects who respond to advertisements, although medical records will generally not be requested

Minimizing the potential for coercion of patients to participate: Because members of the research team are involved in clinical care and research, there is the potential that some patients of the study team may be recruited. It will be made clear to all potential subjects that participation is entirely optional and not a part of regular treatment. The bulk of the recruitment process will occur with the study coordinator, who does not treat patients in any of the clinical venues where recruitment will occur. Overall, the research team is experienced in clinical research and very mindful of the conflict between the dual roles of clinician and researcher. They firmly believe that the safety and desires of the patient take precedence over any research protocol, and work hard to assure their patients that research participation is not required for treatment. In the case where a patient of a study team member is recruited, the consent process and signature on the informed consent document and will be obtained by the study coordinator.

Payment of participants

Participants will receive payments for the initial assessment through the parent study. For the current protocol, they will receive \$10 for each behavioral NIH toolbox and/or Millisecond assessment and BRIEF2 questionnaire before and after treatment as well as \$10 each for the NIH toolbox and/or Millisecond assessment and BRIEF2 completed before the RMT course of treatment, and around week 3 of CBT for CBT+CCT group as well as when completing the fMRI after completing 4 weeks of at home CCT. Participants in the CBT-only group will receive \$10 for the clinical assessment of anxiety and BRIEF2 they may complete at week 3 of CBT. Participants in the CBT+CCT group will receive \$50 per fMRI scan (i.e., up to 3 scans - 1 before, 1 during, and 1 after CBT+CCT may be completed if the subject has not participated in the parent study; up to 2 scans may be completed if the subject has participated in the parent study and already received a pre-CBT+CCT scan). Participants in CBT+CCT group will also receive \$15 for each CBT+CCT session (up to 12 sessions), \$10 for each week of at home CCT training they may complete for two weeks before beginning CBT and during the first 4 weeks of CBT, if they complete at least 4 of the 5 daily trainings. If it is requested for a participant to come back for additional interviews or additional practice sessions in the scanner, we will offer the participant \$15 for these visits as well. Additional \$50 payment(s) will be provided if they are asked to come in again due to any possible technical difficulties with the MRI scanner (but not for repeated scans where participants choose to abort scan and try again at a later date). The parent/guardian will receive the incentive. Payment for all participants will be made in a single payment at the completion of their participation in the study.

6 STUDY INTERVENTION(S) OR EXPERIMENTAL MANIPULATION(S)

6.1 STUDY INTERVENTION(S) OR EXPERIMENTAL MANIPULATION(S) ADMINISTRATION

6.1.1 STUDY INTERVENTION OR EXPERIMENTAL MANIPULATION DESCRIPTION

Cognitive behavioral therapy: The CBT intervention is administered per the protocol of the parent study. It will consist of up to 12 weekly 60-minute sessions of the Coping Cat (ages 7-13) or Cat Project (ages 14-17) manualized programs that have demonstrated efficacy for the treatment of pediatric anxiety disorders (Kendall and Hektke, 2006; Beidas, Benjamin, Puleo, Edmunds and Kendall, 2010). Session content includes: building rapport, identifying anxious feelings/somatic responses and relaxation skills (Sessions 1-2); identifying and challenging anxious thoughts, problem-solving, and self-evaluation/reward (i.e., cognitive restructuring, Sessions 3-5); and, progressive exposure to anxiety provoking situations (sessions 6-12). Parenting content is incorporated into two sessions prior to the initiation of cognitive restructuring and exposure. On some occasions, it may not be clinically appropriate to include a parent in the sessions. This will be determined on an as-needed basis through clinical consensus meeting. Recent research shows that cognitive restructuring and exposure (but not relaxation training, RT) are the “active ingredients” of Coping Cat CBT. Thus, the Cat protocols have been adjusted for the current trial with RT condensed into 2 sessions rather than being delivered over 3-4 sessions as in CAMS). This will maintain fidelity to Coping Cat content, while reducing the increased likelihood of attrition associated with longer treatment protocols. Delivery of CBT intervention over the course of up to 12 (rather than 16) sessions is intended to a) maintain fidelity to Coping Cat content and closely mimic its delivery in CAMS (outcomes assessed at week 12) and b) minimize boredom and the potential effect on anxiety that could be associated with a longer duration control treatment.

Computerized cognitive training: The CCT games are designed to target executive functions such as focused attention, response inhibition, working memory and multiple simultaneous attention to constitute a general executive function training, and activate neural systems associated with executive function/cognitive control. Difficulty of the games will be titrated individually and by session to avoid boredom and progressively activate the functional systems underlying cognitive control, which we hypothesize will optimize participant’s ability to engage in, and thus benefit from, the CBT intervention. These types of games are modelled after existing programs (Brain Powered Games, Giordani et al., 2015; Akili Interactive, Anguera, Gunning and Arean, 2017; Brain HQ www.brainhq.com) that help to improve executive functions and are well-tolerated by participants of varying ages.

6.1.2 ADMINISTRATION AND/OR DOSING

Cognitive behavioral therapy: CBT treatment will be delivered over the course of up to 12 weeks including 60 minutes of face-to-face meeting at the clinical setting. CBT may be delivered via remote video conference if social distancing policies prohibit this type of in-person interaction (e.g., COVID-19). If a remote video conference is not possible, therapy sessions may be scheduled as in-clinic remote visits in the Rachel Upjohn Building.

Computerized cognitive training: The CCT intervention will consist of ~30 minutes of CCT games that may be completed prior to CBT sessions 4-12, to engage cognitive control capacity prior to receipt of CBT. These sessions of CCT may be completed at home if social distancing policies prohibit this type of in-person study activity (e.g., COVID-19). Participants may also receive up to four weeks of at home CCT

(~30 min/day), 5 days per week, for up to two weeks prior to beginning CBT and up to 4 weeks after beginning the 12-week CBT protocol. Participants may complete CCT on an iPad provided by Akili Interactive, or they may complete CCT by downloading the application onto their own Akili-compatible personal device.

6.2 FIDELITY

6.2.1 INTERVENTIONIST TRAINING AND TRACKING

The CBT treatments will be delivered by masters or PhD level therapists trained in these modalities. Supervision will be provided by an expert in the study of CBT in anxiety disorders. Each therapist will treat patients who receive CBT and CBT+CCT. An evaluator, blind to treatment assignment, will assess the patients with the scales described below. The preference will be assessment in person, but, if required, assessment by telephone may be done. In-house form will be used by clinical psychology supervisor to rate therapist adherence to treatment manuals.

Video/audio recording: We are seeking permission to have some assessments and CBT sessions recorded to obtain reliability/fidelity measures. Not all participants will be recorded; this will be determined by needs of the study. The recordings will be done mainly for the K-SADS and/or PARS assessments and therapy sessions.

6.3 MEASURES TO MINIMIZE BIAS: RANDOMIZATION AND BLINDING

There is no randomization in this pilot study. Participants are recruited from the parent study where assignment to the two treatment arms (CBT vs RMT) is stratified based on age and gender, using block randomization to ensure a 2:1 ratio of participants in CBT vs. RMT group (HUM00118950). In this study, we will recruit all possible participants in the RMT group in the parent study to participate in CBT+CCT, and recruit age- and gender-matched participants from CBT group. Efforts will be made to keep therapists blinded to participant group (i.e., CBT+CCT vs. OPT CBT).

6.4 STUDY INTERVENTION/EXPERIMENTAL MANIPULATION ADHERENCE

Assessments (or subsets of questions from these measures) will mainly be completed as part of the parent study and utilized for analysis in this protocol. At each time point, assessments may include:

Assessments Completed by Independent Evaluator– Weeks 0, 1, 3, 6, 9 & 12

- a) PARS
- b) Clinical Global Impressions-Severity and Improvement Scale (CGI); (*Guy and Bonato 1970*).

Assessments by Clinician – Weeks 1-12

- a) CGI (S/I)
- b) Treatment Adherence Rating Scale (TARS) A therapist-administered instrument to assess patient completion of assigned CBT or RMT homework.
- c) C-SSRS (since last visit)
- d) CGAS

Assessments Completed by Subjects – Weeks 1-12

- a) Medication Adherence (also all fMRIs)
- b) MASC – week 1, 3, 6, 9, 12
- c) CDI – week 1, 3, 6, 9, 12
- d) CGI-I (parent report) – week 3, 6, 9, 12.
- e) FAS (parent report) – week 12
- f) BDI (parent report) – week 12
- g) BAI (parent report) – week 12
- h) Beverage and Food Questionnaire – week 3 and 12
- i) GRIT Scale – week 12
- j) SCARED (parent) – week 1, 3, 6, 9, 12
- k) SCARED (child) – week 1, 3, 6, 9, 12
- l) Life Events Checklist – week 12

Other Assessments

- a) CGAS (Independent Evaluator, Week 0 and 12)
- b) Credibility/Expectancy Questionnaire (CEQ; Subject, week 3) – A 6-item scale rating the patient's expectations for treatment success (Devilly & Borkovec, 2000)
- c) Working Alliance Inventory (WAI; Subject, Weeks 6 & 12) – A 12-item scale rating the patient's feelings about their relationship with the therapist (Horvath & Greenberg, 1989) – approximately 5 minutes.
- d) Randomization “guess” form to be completed by Independent Evaluator at week 12 to assess blinding (CBT-only).
- e) Self-Assessment Manikin (SAM; Subject, may be completed before and after each session of CCT) – A 3-item scale rating the patient's feelings of pleasure, arousal, and dominance (Bradley & Lang, 1994) – approximately 2 minutes.
- f) Behavior Rating Inventory of Executive Function, Second Edition (BRIEF2; Parent, pre-RMT course of treatment, pre- and post-CBT course of treatment as well as week 3 of CBT, and when completing fMRI after completion of 4 weeks at home CCT for the CBT+CCT group) – at 63-item parent-report scale assessing executive function of the patient (Gioia, Isquith, Guy, & Kenworthy, 2015) – approximately 10-15 minutes.

6.5 CONCOMITANT THERAPY

Patients will not be taking any psychotropic medications for 4 weeks prior to beginning the study with the exception of stimulants for ADHD. In such cases, patients will be required to maintain a stable dose of stimulant medication for 2 weeks prior to fMRI #1. [name] will manage patient stimulant medications for the duration of the study, meeting with medicated patients 2-4 times, as needed, during the up to 12-week period of study therapy.

6.5.1 RESCUE THERAPY

To address participant crises or unusual needs/circumstances that arise, additional treatment sessions (i.e., ASAP sessions) can be provided to address these needs and facilitate participant retention. A maximum of 2 additional off-protocol sessions is allowed for each phase of the study (CBT or CBT+CCT). These could include psychotherapy or methods outside of prescribed protocol (e.g. motivational interviewing). Additionally, clinical assessment for urgent crisis may be offered and will be scheduled at therapist's behest, participant request or as needed to help reduce dropout. Participants who require more than this limited intervention will be withdrawn and clinical care recommended.

During the study, we will permit medication for 1) insomnia, e.g. trazodone, temazepam, melatonin, or non-benzodiazepine GABA-selective agents (at standard dosages) for as long as needed, and 2) agitation, e.g. lorazepam, clonazepam for up to 14 days. The study psychiatrist will manage initiation and ongoing treatment with these allowable medications during the study. Initiation of allowable “rescue” medications will be considered AEs and data will be collected on them during the scheduled assessments and recorded in the Case Report Forms. NOTE: Initiation of other medications, prior to the end of the study, may be recommended by the study psychiatrist or requested by the patient. In this event, the patient will be withdrawn from the study and referred to clinical care.

7 STUDY INTERVENTION/EXPERIMENTAL MANIPULATION DISCONTINUATION AND PARTICIPANT DISCONTINUATION/WITHDRAWAL

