2.3 RISK/BENEFIT ASSESSMENT

2.3.1 KNOWN POTENTIAL RISKS

2.3.1.1 RISK ASSOCIATED WITH SCREENING AND ASSESSMENTS:

- 1) Risk of boredom or fatigue (likely, not serious). Participants may become tired or bored during the assessments and computerized cognitive testing.

To minimize risk: Participants will be allowed breaks in between testing sections.

- 2) Loss of confidentiality around sensitive information (rare, not serious).

To minimize risk: All subjects are assigned research numbers, and all research information collected is linked to the subject only by this number. Great care is taken to remove all identifying information from research records. A single tracking file contains links to the research records and subject codes. Recruitment tracking files are kept only for the duration of recruitment. Paper records are kept in locked file drawers in a locked room, to which only authorized research personnel have access. Paper records with identifying information (consent form, payment records) are kept in locked file cabinets, physically separate from the research records. Computer records with identifying information are kept on secure, password protected servers. Staff members are trained to scrupulously protect the confidentiality of sensitive information, and take care to limit the printing of documents with identifying information and to avoid unnecessary discussion of subject names. Screening forms for subjects who do not qualify for the study will be destroyed, except for anonymous information unlinkable to the subjects (such as age, gender, and education).

However, if a subject may become eligible in the near future, e.g. they need to wait 1 month after a recent medication change, we will retain certain records so as not to repeat the assessments, with the assent of the potential participant.

- 3) Risk of worsening of anxiety symptoms.

To minimize this risk: Clinically trained study staff will be alert for the emergence of worsening anxiety symptoms, as well as suicidal thoughts amongst participants. Weekly assessments will monitor symptoms, including suicidality, as part of Dimensional Brain Behavior Predictors of CBT Outcomes in Pediatric Anxiety (HUM00118950). In the event of symptom worsening, consultation with [name] may lead to withdrawing the subject so they can receive treatment outside the protocol.

4) Suicide protocol

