For Dimensional Brain Behavior Predictors of CBT Outcomes in Pediatric Anxiety (HUM00118950), the suicide protocol begins with assessment of suicidal thoughts, plans, intentions and behaviors with the C-SSRS (at screening and at each treatment session). If assessment uncovers suicidal plans or intentions or recent behaviors, emergency evaluation will occur, and an appropriate plan of action will be followed, e. g. referral to psychiatric emergency room. [name] will be contacted and will join the decision making process about how to manage the suicidal thoughts or behaviors. See “DISCONTINUATION OF STUDY INTERVENTION/EXPERIMENTAL MANIPULATION” below for criteria about when we will withdraw a patient from the study for suicidality.

2.3.1.2 RISKS ASSOCIATED WITH FMRI SCANNING:

- 1) Discomfort or anxiety (occasional, not serious). There is a minor risk of discomfort or anxiety/panic from being in the confined space of the MRI scanner.

To minimize risk: The risks of discomfort and anxiety will be minimized by custom pads and pillows to make the subject as comfortable as possible. The subject is allowed to communicate with the machine operator via an intercom and may trigger an audible alarm at any time. Before the subject rolls into the bore of the magnetic, he or she is always reminded that they are free to stop the study at any time if they become uncomfortable.

- 2) Peripheral nerve stimulation (rare, not serious). Fast imaging sequences, such as those employed in this study, have the potential to induce peripheral nerve stimulation (PNS). PNS can be described as a light touching sensation on the skin surface and may cause mild discomfort, but is not harmful to the subject.

To minimize risk: The MRI machine is operated within FDA guidelines so the potential for inducing PNS is low.

- 3) Slight dizziness, light-headedness or nausea (rare, not serious). Sometimes subjects report these symptoms during or immediately after the scanning session.

To minimize risk: If a subject feels light-headed, we will have them get up from the scanner bed very slowly, resting with feet dangling for several seconds or more before attempting to stand.

- 4) Magnetic resonance image will reveal a minor or significant lesion in the brain, e. g. a tumor, previously unknown to the subject, and requiring additional follow-up. (rare, serious).

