7.1 DISCONTINUATION OF STUDY INTERVENTION/EXPERIMENTAL MANIPULATION

CBT or CBT+CCT will be stopped in the event of any of the following:

- Suicidal thoughts with specific plans and intentions (Endorse item 4 or 5 on the C-SSRS and the judgment of the clinician that risk of suicide is high and imminent)
- Suicide behaviors during the study period (assessed by C-SSRS)
- Hospitalization required for any psychiatric symptoms
- Symptom worsening: > 25% increased PARS score (referenced to baseline) for more than 2 assessments in 1 week

Reasons for discontinuation will be documented, and all outcome assessments will proceed as scheduled, if possible.

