7.2 PARTICIPANT DISCONTINUATION/WITHDRAWAL FROM THE STUDY

Participants are free to withdraw from participation in the study at any time upon request.

An investigator may discontinue a participant from the study for the following reasons:

- Significant study intervention non-compliance, i.e. inability or unwillingness to complete study intervention or outcome assessments
- Lost-to-follow up; unable to contact subject (see **Section 7.3, Lost to Follow-Up**)
- Any event or medical condition or situation occurs such that continued collection of follow-up study data would not be in the best interest of the participant or might require an additional treatment that would confound the interpretation of the study
- The participant meets an exclusion criterion (either newly developed or not previously recognized) that precludes further study participation
- The study is suspended or canceled

The reason for participant discontinuation or withdrawal from the study will be recorded on the Case Report Form (CRF). Subjects who sign the informed consent form and are randomized but do not receive the study intervention may be replaced. Subjects who sign the informed consent form, and are randomized and

receive the study intervention, and subsequently withdraw, or are discontinued from the study, will be replaced.

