8.2 SAFETY ASSESSMENTS

- **fMRI Safety Screen form** in order to ensure that there are no contraindications for fMRI. This form is provided by the fMRI lab and is not included within study documentation. The most current version of this screening form will be used at all times to ensure the safety of participants undergoing fMRI.
- **Columbia Suicide Severity Rating Scale**, present/lifetime version (Posner, Oquendo et al. 2007). A clinician-rated scale assessing suicidal ideation and behavior.
- **Pediatric Anxiety Rating Scale (PARS)**. A clinician-administered assessment to rate the severity of anxiety symptoms associated with common DSM-V anxiety disorders (social phobia, separation anxiety disorder, and generalized anxiety disorder) in children. Total scores on this scale range from 0 to 30, with scores above 13 indicating clinically meaningful anxiety. Approximately 20–30 minutes. Symptom worsening: > 25% increased PARS score (referenced to baseline) for more than 2 assessments in 1 week

Any safety-related assessments (C-SSRS administered through the parent study, fMRI screening) or primary outcome measure (PARS– independent assessor may administer at weeks 0, 1, 3, 6, 9, and 12; missed week 9 will not be reported as a deviation) that are missed for a study visit/week of therapy a participant completed will be reported to the IRB as a protocol deviation. For the independent assessments, we will accept a window of \pm 1 week. For CBT+CCT group, the 3-week, 6-week, and 9-week PARS assessments are completed under this protocol only, and a PARS assessment may be completed under this protocol prior to beginning at-home CCT treatment if there have been more than about 6 weeks since the RMT week 12 PARS. For the CBT-only group, the 3-week PARS assessment is completed under this protocol only. However, for the other assessments, missing or late assessments will not be reported as protocol deviations unless they constitute > 10% of the total assessments. In order to accommodate inevitable scheduling conflicts, holidays, etc., participants will be allowed to miss up to 4 sessions of therapy, and the sessions must be completed within 16 weeks. These allowances should affect neither the scientific integrity nor the safety monitoring provisions of the protocol.

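### Section 7.1 keeps assessing youth whose treatment is stopped, but Sections 2.3.1.1, 5.3, 6.5.1 and 7.2 withdraw youth for the same or related events with no such rule, so week-12 anxiety data may be lost selectively

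*Combined protocol and SAP*

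**What the plan says.** Section 7.1 lists events that end CBT or CBT+CCT: high-risk suicidal thoughts, suicidal behavior, psychiatric hospitalization, and worsening, defined as "Symptom worsening: > 25% increased PARS score (referenced to baseline) for more than 2 assessments in 1 week". It then separates stopping treatment from leaving the study: "Reasons for discontinuation will be documented, and all outcome assessments will proceed as scheduled, if possible".

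Other sections deal with the same or neighboring events differently:

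- Section 2.3.1.1 (suicide protocol) sends the reader to the discontinuation section "for criteria about when we will withdraw a patient from the study for suicidality".
- Section 2.3.1.1 (worsening of anxiety) says that consultation after worsening "may lead to withdrawing the subject so they can receive treatment outside the protocol".
- Sections 5.3 and 6.5.1, on starting a medication other than the permitted ones: "In this event, the patient will be withdrawn from the study and referred to clinical care".
- Section 6.5.1, on needing more than two off-protocol sessions per phase: "Participants who require more than this limited intervention will be withdrawn and clinical care recommended".
- Section 7.2 lets the investigator discontinue a participant for an event that "might require an additional treatment that would confound the interpretation of the study". It also says that treated participants who withdraw or are discontinued are to be replaced.

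Section 8.2 makes safety assessments and PARS ratings reportable when they are ones "that are missed for a study visit/week of therapy a participant completed will be reported to the IRB as a protocol deviation".

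Section 9.3.3 analyzes PARS by repeated-measures ANOVA and response by chi-square. It does not say how youth without a week-12 rating are counted.

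**The concern.** A youth who meets the suicidality criteria stays under assessment if staff follow Section 7.1, and leaves the study if they follow the description in Section 2.3.1.1. A youth who worsens may be handled either way. A youth who starts another medication, or needs more than the allowed extra sessions, falls only under a withdrawal rule, and nothing says that the scheduled ratings continue.

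Crisis care, added medication and worsening are plausibly signs of poor response. If ratings end at those points, poor outcomes are under-represented in the week-12 PARS change and in the responder table, and the arm that loses more of them looks better than it is. Replacing the lost youth restores the head count but not the lost outcomes.

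PARS is a secondary endpoint in Sections 3 and 9.1, yet Section 4.1 names clinician-rated anxiety change as the primary outcome variable and Section 8.2 calls PARS the primary outcome measure. Section 9.2 says the pilot is meant to supply effect sizes for a later application, so a bias here would carry forward.

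**Working it through.** **1. The rules side by side**

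| Event | Section 7.1 | Elsewhere | Relation |
|---|---|---|---|
| Suicidality criteria | stop treatment, keep assessing | 2.3.1.1: withdrawal from the study | direct conflict |
| PARS worsening | stop treatment, keep assessing | 2.3.1.1: may withdraw | discretionary overlap |
| Other medication started | not listed | 5.3, 6.5.1: withdrawn from the study | no continued-assessment rule |
| More than two extra sessions | not listed | 6.5.1: withdrawn (from what is not stated) | no continued-assessment rule |
| Confounding additional treatment | not listed | 7.2: may discontinue from the study | no continued-assessment rule |

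**2. The plan's own attrition figure.** Section 5 gives 36 CBT and 18 CBT+CCT, 96.2% therapy retention and 89% for fMRI motion, and expects 32 and 14 with usable data (46 in all).

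- 54 × 0.962 × 0.89 = 46.2, against 46 stated.
- By arm, 36 × 0.962 × 0.89 = 30.8 (stated 32) and 18 × 0.962 × 0.89 = 15.4 (stated 14).

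The total reproduces. Each arm is within two youth, though this formula does not give either arm exactly. Only the 96.2% matters for PARS.

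**3. Expected loss from all causes**

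- Total: 54 × (1 − 0.962) = 2.05.
- CBT: 36 × 0.038 = 1.37.
- CBT+CCT: 18 × 0.038 = 0.68.
- Binomial for CBT+CCT (n = 18, p = 0.038): P(0) = 0.962^18 = 0.498 and P(1) = 18 × 0.038 × 0.962^17 = 0.354, so P(2 or more) is about 15%. P(3 or more) is about 3%.

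**4. Effect on the response rate.** Assumed: true response 10/18 and 20/36 (both 55.6%), every lost youth a non-responder, and lost youth left out of the table.

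| Lost | CBT+CCT | Shift | CBT | Shift |
|---|---|---|---|---|
| 1 | 10/17 = 58.8% | +3.3 | 20/35 = 57.1% | +1.6 |
| 2 | 10/16 = 62.5% | +6.9 | 20/34 = 58.8% | +3.3 |

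Equal proportional losses cancel: one of 18 and two of 36 give 10/17 = 20/34 = 58.8%.

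Replacement hardly helps. With two lost and replaced at the true rate, the expected value is (10 + 2 × 10/18)/18 = 61.7%, against 62.5% without replacement.

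For scale, the standard error of the difference is √[0.556 × 0.444 × (1/18 + 1/36)] = 0.143, about 14 points.

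**5. Effect on mean PARS change.** If change is normally distributed and the worst fraction q of an arm is missing, the arm mean moves by φ(z_q)/(1 − q) standard deviations in the favorable direction. For q = 0.038 this is 0.086 SD.

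**The case against.** Much can be said for the plan. The only direct conflict is the suicidality cross-reference; the worsening sentence in Section 2.3.1.1 is discretionary. The medication and extra-session triggers are not in the Section 7.1 list, so they do not contradict it. They fit a deliberate division in which Section 7.1 stops treatment and Section 7.2 ends participation, including for confounding treatment. This stands: for those triggers the point is a gap with a bias risk, not an internal contradiction.

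Nor do the documents say outright that ratings cease at withdrawal. That is an inference from the withdrawal wording, from the replacement rule in Section 7.2 and from the absence of any rule retaining these youth. Medication may also be started at the patient's request, so not every withdrawal marks a treatment failure.

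A reader might infer from Section 8.2 that ratings missed after treatment stops go untracked. The text does not support that. It governs deviation reporting, while Sections 7.1 and 7.2 record reasons and Section 9.3.4 lists measures by time point.

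A reader might also infer that analysis cannot repair the loss. That goes too far: withdrawn youth could be counted as non-responders, and PARS ratings before withdrawal could inform a longitudinal model. But Section 9 specifies neither, and neither supplies the missing week-12 rating.

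**Conclusion.** The point holds in limited form. The suicidality wording conflicts between Sections 2.3.1.1 and 7.1, the worsening rules overlap, and the continued-assessment rule is not extended to youth withdrawn under Sections 5.3, 6.5.1 or 7.2. Selective loss of week-12 PARS and responder data is therefore possible, and replacement would not undo it.

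The stronger reading, that the worst outcomes will be lost and that a sizable false benefit follows, is not supported. It needs ratings to stop at every withdrawal, every loss to be a non-responder, and losses to fall mainly in one arm. The expected loss is under one youth in CBT+CCT, and the shift of 3 to 7 points for one or two losses is small beside a standard error of about 14 points. The figures also assume that the parent study's retention applies to both groups here; the 55.6% response rate is illustrative. The change is worth making because it is cheap and the small arm is sensitive to single losses.

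**What to change.** - Reconcile Sections 2.3.1.1, 5.3, 6.5.1, 7.1 and 7.2 so that each withdrawal sentence says whether study treatment stops, data collection stops, or both. Leave every clinical trigger and rescue rule unchanged. Bring the suicide-protocol cross-reference into line with Section 7.1.
- State that the remaining scheduled independent-evaluator PARS and Clinical Global Impressions ratings through week 12 are collected, unless consent or assent is withdrawn or continued collection is not in the participant's interest (the Section 7.2 ground).
- State in Sections 7.2 and 9.3.3 that a participant who is replaced stays in the PARS and responder analyses.
- Extend the Section 8.2 deviation rule to a missed PARS in participants who are off treatment.

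**Cost.** Protocol wording and a few interviews already on the schedule; Section 6.2.1 allows assessment by telephone. Some late ratings will reflect outside treatment and need a flag. The wording must also be aligned with the parent study. Section 6.4 says most assessments are done there, Section 5.1 requires continued enrollment and eligibility in it, and Section 8.2 does not list the week-12 PARS among the ratings collected under this protocol only. Whether that rating can continue after withdrawal may depend on the parent protocol, which is not among these documents.
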